2 GENERAL CONSIDERATIONS FOR DATA ANALYSES

2.1 Analysis Data Sets

Efficacy and safety analyses will be performed on data from the following analysis sets:

- Enrolled patients set (EPS) will consist of all patients who signed the informed consent. This data set will be used to summarize the patient disposition data.
- Modified intention to treat set (modified ITTS) is defined as all patients who have been randomized to study treatment, have received at least one dose of study medication, and have sufficient evaluable data for endpoint ascertainment during follow up. For clarity, patients with no evaluable data for a particular outcome during follow up will be excluded from the analyses of these respective endpoints. In patients who undergo initiation of intravenous home inotropic support and/or receive left ventricular assist device or heart transplant during the study or who are started on a prohibited medication (open label SGLT-2is), for efficacy analyses, the last available data point(s) prior to these events will be used. Subjects will be analyzed according to the randomization group. The modified ITTS data set will be used for the primary, secondary, and selected exploratory (NYHA class, loop diuretic dose) efficacy endpoints.
- On-treatment set (OTS) includes all subjects in the modified ITTS. Primary and secondary endpoint measurements will be excluded for the follow-up time point(s) when subjects were temporarily or permanently off the study drug at the time the corresponding measurements were obtained. The OTS data set will be used for a sensitivity analyses for the primary, secondary, and selected exploratory (NYHA class, loop diuretic dose) efficacy endpoints.
- The per protocol set (PPS) includes all subjects in the modified ITTS who did not have any major protocol deviations. Major protocol deviations, which are detailed in section 2.2, will be determined prior to unblinding of treatment groups. Subjects will be summarized according to actual treatment received regardless of the allocated treatment. This will be used for a sensitivity analysis for the primary efficacy endpoints only.

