2.3 Strata, Covariates, and pre-specified subgroup analyses

All efficacy and safety endpoints will be analyzed in the entire cohort, and then within the subgroups of patients with and without diabetes. Analyses for the primary and secondary endpoints will be adjusted for the corresponding baseline measurements as well as history of diabetes (DM), eGFR, and age. A sensitivity analysis will be conducted for each endpoint adjusting for the following additional baseline covariates: AFib type (No AFib, persistent/permanent AFib, paroxysmal AFib) and LVEF (as continuous variable). Restricted cubic splines will be used for continuous variables to accommodate non-linear effects.

Additional sensitivity analysis will repeat the primary analysis but will also include site as a random effect to account for potential clustering by enrolling center. A different sensitivity analysis will use the same model as the primary analysis, but adjust only for the corresponding baseline measurements, without additional covariates.

Additionally, the following pre-specified subgroup analyses will be performed for the primary endpoints (stratified by the baseline variables below):

- Baseline NTproBNP (< median, ≥ median)
- Baseline LVEF (≤30%, > 30%)
- Atrial fibrillation type (No AFib, permanent/persistent AFib, paroxysmal AFib)
- Baseline KCCQ overall summary score (<70, ≥70)
- Baseline eGFR (<60, ≥60 mL/min/1.73 m²)
- Type of cardiomyopathy (ischemic, non-ischemic)
- Age (<65, ≥65)
- Sex (male, female)
- Race (white, black, other)
- Baseline RAASi type (ARNI, ACE/ ARB, neither)
- Loop diuretic dose (Furosemide equivalent mean daily dose: \leq 40 mg, >40 mg)

Subgroup analyses will be carried out by augmenting the primary analysis model with terms for subgroup and a subgroup-by-treatment interaction. Adjusted point estimates and 95% confidence intervals will be calculated for the effect of dapagliflozin compared with placebo within each subgroup. An interaction p-value will be provided.

Due to the large number of study sites and the expected low number of patients per site, site effects will not be explored, although study site will be included as a random effect in efficacy sensitivity analyses to account for within-site correlations, as specified above.

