2.7 Data Handling Conventions and Transformations

Diabetes duration will be calculated as (Consent date – DM diagnosis date) / 365.25. It will be rounded to the whole year.

Body mass index (BMI) will be calculated as weight (kg) / [height (m)]². It will be displayed to 1 decimal place in listings, but will not be rounded or truncated prior to summarization

Estimated glomerular filtration rate (eGFR) will be calculated using the MDRD-4 equation: GFR in mL/min per $1.73 \text{ m}^2 = 175 \text{ x}$ SerumCr^{-1.154} x age^{-0.203} x 1.212 (if patient is African American) x 0.742 (if female). Patients with missing data in Creatinine Serum, age, race, or gender will not have eGFR calculated.

If urine microalbumin value is reported as being too high for the laboratory to calculate a UACR, 5000 mg value for UACR will be used.

3 Analyses of Baseline Characteristics

Patient demographics, baseline clinical characteristics, medical histories, and baseline labs will be described overall and by treatment group. Continuous measures will be summarized by mean \pm standard deviation and compared using Student's T-tests. Categorical variables will be summarized by frequency and percent and compared using χ^2 or Fisher's exact tests, as appropriate.

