5.1.1 The first dual primary endpoint: NT pro-BNP

Mean, standard deviation, median, and interquartile range (IQR) will be reported for NT pro-BNP and for its change from baseline at 6- and 12-week follow-up, for the entire cohort and by treatment group.

A generalized linear mixed model will be used to estimate the effect of treatment on the average of 6- and 12week NT pro-BNP values, adjusting for log baseline NT pro-BNP, history of DM, eGFR, and age. Random effects will be included for patient. A gamma distribution and log link function will be used to account for the skewed nature of NT pro-BNP. The model is as follows:

$$\begin{split} E(y_{ijk}) &= \mu_{ijk}, \qquad Var(y_{ijk}) = \mu_{ijk}^2 \varphi, \\ \log(\mu_{ijk}) &= \beta_0 + \beta_1 Trt_{ij} + \beta_2 t_k + \beta_3 Trt_{ij} * t_k + \beta x + \gamma_{ij}, \end{split}$$

$$\gamma_{ij} \sim N(0, \sigma^2),$$

where, μ_{ijk} denotes the expected NT pro-BNP level for patient j from site i at time k, Trt_{ij} is a 0/1 variable denoting treatment group (dapagliflozin vs. placebo), t_k indicates the follow-up assessment time ($t_6 = 0, t_{12} = 1$), and **x** is the design matrix for log baseline NT pro-BNP, age, DM, and baseline eGFR. γ_{ij} are patient random effects with variance σ^2 . ϕ is a scale factor. With this parameterization, the quantity $exp(\beta_1 + \beta_3/2)$ represents the expected relative effect of dapagliflozin vs. placebo on the geometric mean of 6- and 12-week NT pro-BNP. The quantities $exp(\beta_1)$ and $exp(\beta_1 + \beta_3)$ represent the corresponding relative effects at 6 and 12 weeks, respectively.

A sensitivity analysis will be performed using the same model additionally adjusting for AFib type (No AFib, persistent/permanent AFib, paroxysmal AFib) and baseline LVEF.

Additional sensitivity analysis will repeat the primary analysis but will also include site as a random effect to account for potential clustering by enrolling center. A different sensitivity analysis will use the same model as the primary analysis, but adjust only for the corresponding baseline measurements, without additional covariates.

Finally, another sensitivity analysis will repeat the primary analysis on the on-treatment set (OTS).

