5.1.2 The second dual primary endpoint: meaningful change in NT pro-BNP or KCCQ

Unadjusted proportions of patients achieving meaningful change in NT pro-BNP or KCCQ (a \geq 5-point increase in average of 6- and 12-week KCCQ overall summary scores or a \geq 20% decrease in average of 6- and 12-week NT pro-BNP), will be reported for the treatment group and placebo group. A mixed-effect logistic regression model will be used to assess the effect of treatment on the proportion of patients achieving meaningful change on 6 and 12 weeks average KCCQ and NT pro-BNP. Models will be adjusted for log baseline NT pro-BNP, baseline KCCQ overall summary score, history of DM, eGFR, and age. The model is specified as follows:

 $E(y_{ij}) = p_{ij}, \qquad Var(y_{ij}) = p_{ij}(1 - p_{ij})$

 $logit(p_{ij}) = \beta_0 + \beta_1 Trt_{ij} + \beta x$

where p_{ij} denotes the expected probability for patient j from site i achieving meaningful change in NT pro-BNP or KCCQ, Trt_{ij} is a 0/1 variable denoting treatment group (dapagliflozin vs. placebo), \mathbf{x} is the design matrix for log baseline NT pro-BNP, baseline KCCQ summary score, history of DM, eGFR, and age. With this parameterization, the quantity $exp(\beta_1)$ represents the odds ratio of achieving meaningful change in the treatment group vs. the placebo group.

A sensitivity analysis will be performed using the same model additionally adjusting for AFib type (No AFib, persistent/permanent AFib, paroxysmal AFib) and baseline LVEF.

Additional sensitivity analysis will repeat the primary analysis but will also include site as a random effect to account for potential clustering by enrolling center. A different sensitivity analysis will use the same model as the primary analysis, but adjust only for the corresponding baseline measurements, without additional covariates.

Additional sensitivity analyses will repeat the primary analysis on the on-treatment set (OTS); and repeat the primary analysis excluding patients with baseline KCCQ overall summary score of over 90 (as these patients will have a limited opportunity for improvement in KCCQ).

Additional supportive analyses will be performed evaluating the empirical cumulative distribution function for change in NT pro-BNP, and for change in KCCQ overall summary score at 6 weeks and at 12 weeks (responder curves).

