6.2	Patients with absence of baseline NT-proBNP data at both screening and randomization visits	Other	Excluded from the NT- proBNP analyses
6.3	Patients with no NT-proBNP values after randomization	Other	Excluded from the NT- proBNP analyses
6.4	Patients with absence of baseline KCCQ summary score at randomization visit	Other	Excluded from the KCCQ analyses
6.5	Patients with no KCCQ overall summary score after randomization	Other	Excluded from KCCQ analyses
6.6	Patients with absence of baseline 6-minute walk assessment at randomization visit	Other	Excluded from the 6- minute walk analyses
6.7	Patients with no 6-minute walk assessment after randomization	Other	Excluded from 6- minute walk analyses
6.8	Patients with missing values in the covariates: age, gender, Hx AFib, AFib type, Hx DM, eGFR at randomization, lvef at randomization	Other	No exclusion from PPS Excluded from the first and second primary analysis

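### SAP 9.2 row 6.8 drops patients with missing AFib history, AFib type or LVEF from both primary analyses, although neither primary model uses those variables

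*SAP*

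**What the plan says.** Row 6.8 of SAP 9.2 defines a deviation as "Patients with missing values in the covariates: age, gender, Hx AFib, AFib type, Hx DM, eGFR at randomization, lvef at randomization". Such patients stay in the per-protocol set but are "Excluded from the first and second primary analysis". The row leaves no room for judgement, whereas most eligibility rows in the same table are left to individual decision.

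The primary models are set out elsewhere:

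- SAP 5.1.1 estimates the NT-proBNP effect "adjusting for log baseline NT pro-BNP, history of DM, eGFR, and age".
- SAP 5.1.2, for the responder endpoint, says: "Models will be adjusted for log baseline NT pro-BNP, baseline KCCQ overall summary score, history of DM, eGFR, and age".
- SAP 2.3 gives the general rule that primary and secondary analyses "will be adjusted for the corresponding baseline measurements as well as history of diabetes (DM), eGFR, and age". It then adds: "A sensitivity analysis will be conducted for each endpoint adjusting for the following additional baseline covariates: AFib type", with LVEF as the second added variable. Both variables also define subgroups.

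For the analysed population, SAP 2.1 requires randomisation, at least one dose and evaluable follow-up data, and states that "patients with no evaluable data for a particular outcome during follow up will be excluded from the analyses of these respective endpoints". SAP 2.6 asks, for the first primary endpoint, for a baseline and at least one later assessment.

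**The concern.** A complete-case rule makes sense for variables the model needs, because a patient with a missing covariate cannot be fitted without imputation. Row 6.8 goes further and makes entry to the main analysis depend on variables used only in a sensitivity model and in subgroups.

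There are two consequences. First, any patient with usable outcomes and every primary-model covariate, but no recorded AFib status or LVEF, would be lost for no stated reason. If such patients exist, that is a further step away from intention to treat. Because these are baseline variables, the cost is mainly precision rather than bias. Second, the SAP supports two different primary samples: one from 2.1, 2.6 and 5.1, and a possibly smaller one from 9.2. Which patients enter the primary analysis should not depend on the section the programmer follows.

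**Working it through.** **Step 1: compare the row with the models.** Each of the seven variables in row 6.8 is checked against SAP 5.1.1 and 5.1.2.

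| Variable in row 6.8 | In first primary model | In second primary model | Needed for the primary analysis? |
|---|---|---|---|
| Age | yes | yes | yes |
| Diabetes history | yes | yes | yes |
| eGFR | yes | yes | yes |
| Gender | no | no | indirectly, through eGFR |
| AFib history | no | no | no |
| AFib type | no | no | no (sensitivity and subgroup only) |
| LVEF | no | no | no (sensitivity and subgroup only) |

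Gender belongs in the list because SAP 2.7 states: "Patients with missing data in Creatinine Serum, age, race, or gender will not have eGFR calculated". So four of the seven variables are justified and three are not. AFib history, as a variable separate from AFib type, is in no planned efficacy model.

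**Step 2: compare the row with the population rules.** SAP 2.1 and 2.6 depend on dosing, a baseline assessment and follow-up data. Neither mentions AFib or LVEF. SAP 2.2 sends the reader to 9.2 for the deviation criteria, so row 6.8 is an operative rule.

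**Step 3: check the row against itself.** Row 6.8 keeps the patient in the per-protocol set. SAP 2.1 defines that set as part of the modified ITT set, and SAP 5.1 repeats the same models on it. The per-protocol run could therefore include patients whom the primary run leaves out.

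**Step 4: size.** The plan gives no figure to reproduce and no missingness rate. Only patients who lack AFib or LVEF data, and nothing else the primary models need, count towards the loss. Call their number k. With 2 × 110 = 220 evaluable patients (SAP 1.3) and allocation staying about equal, the relative widening of the standard error is √(220/(220 − k)) − 1:

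- k = 1: √(220/219) − 1 = 0.23%
- k = 3: √(220/217) − 1 = 0.69%
- k = 5: √(220/215) − 1 = 1.16%

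In terms of power for the second endpoint (30% against 48%, two-sided 5%), the usual two-proportion normal approximation gives 78.5% at 110 per group; the SAP states 80%. At 108 per group, an assumed loss of about 2%, it gives 77.8%. All these losses are illustrations, not estimates.

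**The case against.** The strongest reply has four parts.

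- **Almost nobody would be affected.** LVEF of 40% or less on imaging is required for entry (Protocol 4.1), permanent-AF status is needed to apply the natriuretic peptide thresholds (Protocol 4.2 footnotes), and a patient without AFib falls in a defined category of AFib type. This stands, and it is why the point is minor.
- **Silence in 2.1 and 2.6 is not contradiction.** Section 9.2 is the designated place for exclusion rules. This is fair as far as it goes. The conflict that matters is with the model specifications in 5.1.1, 5.1.2 and 2.3, which give these variables no role in the primary fit.
- **A common sample may have been intended.** Using the same patients in the primary and the AFib/LVEF-adjusted models is a defensible choice, but the SAP does not state it. SAP 5.2 plans the same adjusted run for every secondary endpoint, yet row 6.8 names only the primary analyses. That argument is not decisive: LVEF and AFib subgroups are mandatory only for the primary endpoints (2.3) and optional for the secondary ones (5.4), which could explain the narrower wording.
- **The row may be shorthand** for the whole family of primary-endpoint analyses, with each model dropping patients who lack its own covariates. That would be sensible, but the row does not say so. It names the first and second primary analyses and pools all seven variables.

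**Conclusion.** The concern holds. As written, row 6.8 excludes patients from both primary analyses over three variables that neither primary model uses, and no other section of the SAP supports the exclusion. The mismatch is certain from the text. Its effect on the result is unknown and probably small: about 0.23% on the standard error for each patient lost, assuming 220 evaluable patients and balanced losses. Little bias is expected, since the variables are measured before treatment. Severity is minor, but the rule decides who is in the primary analysis and should be settled before unblinding.

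**What to change.** Before unblinding, make these changes to the SAP:

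1. Limit row 6.8 to age, diabetes history, and eGFR with the components that SAP 2.7 requires (creatinine, age, race, gender). Baseline NT-proBNP and KCCQ are already covered by rows 6.1, 6.2 and 6.4.
2. Require AFib type and LVEF only in the sensitivity and subgroup analyses that use them, and drop AFib history as a separate condition.
3. If like-for-like comparison with the AFib/LVEF-adjusted model is wanted, refit the primary model on patients complete for those variables as a supportive run.

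Two side items can go into the same edit, although the finding does not rest on them. The row refers to LVEF at randomisation, but the study plan (Protocol Table 1) schedules no LVEF measurement. The label should be the most recent value before randomisation, in line with SAP 3.2.2. Optionally, the screening eGFR could stand in for a missing randomisation value, as row 6.1 already allows for NT-proBNP.

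The cost is SAP wording only. No new data are needed, and the main change can only keep patients in the primary analysis.
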